In our theoretical model, mindfulness training directed at eating behavior strengthens the ability to tolerate negative states (e.g., cravings for foods incompatible with one’s dietary goals) without enacting maladaptive automatic behaviors (e.g., eating in response to craving), providing a potentially powerful tool for facilitating healthy eating behavior. Given the relations above, we focus on cravings as a primary mechanism for overeating. Our intervention choice, mindfulness, may have the unique ability to help people tolerate cravings and reduce compulsive eating, as our pilot data suggests.

Mindfulness training can also bolster adaptive stress management, and thereby holds the potential to reduce stress-eating, which is associated with poorer metabolic health. . People who report stress-eating may be more vulnerable to developing obesity and metabolic syndrome.¹⁸ Mindfulness is associated with lower stress-eating in people with diabetes, cross-sectionally.⁸ Our mindfulness-based intervention will include MBSR-based stress management components and Mindfulness Based Eating Awareness Training,¹⁹ which, taken together, act on stress-eating behavior, as well as eating in response to any negative emotions (emotional eating). Improving stress management skills may also directly influence blood glucose levels in T2DM via improvements in maladaptive neuroendocrine responses, as stress hormone responses counteract insulin thereby increasing blood glucose levels..^{20,21} Strengthening adaptive coping responses to stress may also facilitate health behavior such as adhering to medication, diet, and exercise regimens.^{22,23}

There are important new challenges in optimizing mindfulness-based interventions for diet change. This proposal builds on our group’s study of the effects of including mindfulness-based eating and stress management to achieve weight loss and improve metabolic parameters in persons with obesity, but without T2DM (SHINE). While we found evidence of benefits in weight, lipids, and fasting

glucose, we also found variability in participant outcomes by teacher that highlights the need to further optimize the intervention manual/approach.

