3. STUDY DESIGN

This is a two-phase study. Both phases will use a randomized, controlled trial design. After pilot testing in the first phase, the second phase will include employing an adaptive intervention design in the post-treatment phase to test optimization of the maintenance intervention (i.e. assigning maintenance intensity/dose based on how a participant is doing).

We will use ecological momentary assessment (EMA) methods to measure eating in response to difficult emotions and/or food cravings. In the R61 phase, we will ensure this measure is appropriate for further testing and assess the impact of the MBI components on our hypothesized behavioral mechanisms in N=60 community-dwelling adults with T2DM. We plan 3 waves of 20 persons each with 12 weekly sessions followed by 3 monthly maintenance sessions, to be held at UCSF Osher Center for Integrative medicine. All participants will attend an in-person group course providing education on basic behavioral strategies for diet and physical activity. Participants will be randomized (1:1 ratio) to receive this education alone (Ed) or this same material with added MBI components (Ed+MBI). We will also pilot test two levels of intensity of maintenance phase intervention (monthly group meetings alone or supplemented by individualized attention) to prepare them for R33 testing. Assessments will be done at 0, 3 and 6 months. Study participation lasts approximately 8 months per participant. The R61 phase of the study is 2 years total.

We plan an R33 phase trial in which 120 persons with T2DM will be randomized (using a 1:2 ratio) to Ed or Ed+MBI conditions and followed for 12 months, including a 9-month maintenance phase. We will test the robustness of the effect of MBI components on our proposed behavioral mechanisms, and on dietary adherence, as well as preliminary effect sizes on weight and glycemic control. We will use an innovative adaptive intervention design to optimize maintenance phase intensity, which we believe may be key to augment the MBI effects. For this phase, assessments will be conducted at 0, 3, 6 and 12 months, with study participation lasting approximately 14 months per participant, and the entire r33 phase lasting 3 years.

In both phases, randomization will be done using blocked randomization to ensure approximately equal group sizes, with randomly selected block sizes and will be stratified by BMI (below and above

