5. STUDY INTERVENTIONS

5.1 Interventions, Administration, and Duration

All participants will attend 12-weekly study intervention classes based on their random assignment: either Education alone (Ed) or Education+Mindfulness (Ed+MBI). Study groups will be held at the UCSF Osher Center for Integrative Medicine. Both groups will learn and follow a carbohydrate-restricted (CR) diet for T2DM, and will participate in maintenance phase activities. If assigned to Ed+MBI, they will also learn and practice mindfulness-based skills.

Maintenance phase: In the R61 phase, we will pilot test two levels of intensity of maintenance phase intervention (monthly group meetings alone or supplemented by individualized attention) to prepare them for R33 testing.

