5.2 Handling of Study Interventions

Intervention content for the Ed program: All participants will receive instruction in the CR diet and basic behavioral strategies in a weekly, in-person, group sessions meeting for 1 to 1.25 hours for 12 weeks. A nutritionist or health professional with experience implementing CR diets with people with T2DM will train participants in how to follow the study diet, utilizing our study manual and curriculum materials developed by the team based on prior studies. The study diet has approximately 10% of kcal coming from carbohydrate, typically 50 grams/day or fewer, not including fiber. Participants will be encouraged to eat a normal amount of protein, typically about 80-100 grams/day (about 20-25% of calories), and the rest of their calories from fat. Foods that are encouraged include green leafy and other non-starchy vegetables, nuts, seeds, oils (especially olive oil), fish, poultry, tofu, and avocados. Other foods consistent with the diet include berries (in modest amounts), meats, eggs, and cheese. Key foods to minimize include any sugar-sweetened foods or beverages, bread, pasta, potatoes, highly processed packaged foods, and other starchy foods. We have developed extensive

materials to educate participants in practical and nutritionally sound approaches to a carbohydrate restricted diet.

Cognitive and behavioral components: All participants will receive core behavioral intervention components derived from the Diabetes Prevention Program (DPP),³⁶ which include goal-setting and self-monitoring of weight, diet, and physical activity..

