Participants will be randomized in a 1:1 fashion to one of two study groups (Ed or Ed+MBI), using block sizes of 4-6, and stratifying by BMI (above and below BMI of 25). We do not have a sample size goal for each stratum, but we want to ensure that the two arms have approximately equal numbers of normal weight participants.

Randomization to intervention group and maintenance phase track will be done via the Salesforce database. The randomization table will be programmed by a database manager, who is not otherwise involved in any enrollment or other participant procedures. Randomization will be done via the Project Director, [name], who will not have access to the randomization table. When a participant ID number is entered into the database by study staff, a group assignment is revealed. This provides a computerized group assignment that cannot be altered by study staff and the group assigned is immediately recorded in the study database.

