9.6 Data Analyses

Overall analysis approach: Preliminary analysis will be performed to confirm that key data variables are clean and complete in prepared datasets. Baseline patient characteristics will be compared between intervention groups to assess whether important characteristics were evenly distributed during randomization. General analytic approaches will include estimation of odds ratios and risk differences plus chi-square tests for categorical variables compared across groups, rates of change with confidence intervals plus McNemar's test for categorical variables compared pre/post-intervention within groups, and t-tests and multiple regression for comparing continuous variables between groups. Secondary analyses will use random-intercept-random-slope mixed effects models for all repeated measures over time, with linear splines used to estimate initial improvements, subsequent maintenance, and possible eventual backsliding.

The principal analysis will use intent-to-treat methods in which all observations will be included for individuals based on initial group assignment, regardless of adherence to the treatment protocol. As a secondary analytic method, we will also perform as-treated analyses with those who attend at least 2/3

of weekly group sessions (8/12). We recognize the challenge of missing data in assessing clinical trial outcomes. We will take extensive steps to limit missing data. Our team has extensive experience in study retention; in our SUCCEED T2DM study, outcome assessment was completed in 97% of participants at 12 weeks. For our primary mechanism measure, eating in response to cravings using EMA, data can be obtained even for persons who move or have to travel. Finally, we will employ mixed-effects models and multiple imputation methods to address missing data if there is still a substantial amount.

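### Both arms are taught in classes and the team has seen outcomes vary by teacher, yet the plan does not say how diet teachers are assigned, and its analysis and sample size treat participants as independent

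*Combined protocol and SAP*

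**What the plan says.** **Teacher variability.** Section 2.2, on the team's previous study in people with obesity but without type 2 diabetes, says "we also found variability in participant outcomes by teacher that highlights the need to further optimize the intervention manual/approach". The response given there is further work on the manual and approach.

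**Group delivery.** Section 3 says of R61: "We plan 3 waves of 20 persons each with 12 weekly sessions followed by 3 monthly maintenance sessions". Allocation is 1:1. Section 5.1 says: "All participants will attend 12-weekly study intervention classes based on their random assignment".

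**Who teaches.** Section 5.2 says of the diet, which both arms receive: "A nutritionist or health professional with experience implementing CR diets with people with T2DM will train participants in how to follow the study diet". It gives neither the number of such teachers nor whether one person serves both arms of a wave. Only Ed+MBI has a mindfulness instructor, for an extra hour ahead of each diet session.

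**Analysis and sample size.** Section 9.6 plans "t-tests and multiple regression for comparing continuous variables between groups", and makes the between-group comparison of change from baseline the primary analysis. Its mixed models are secondary and handle each person's repeated measurements. No class, teacher or wave term is named. Section 9.2 applies no allowance for clustering.

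**The concern.** Participants in a class share a teacher, a discussion and a peer group, so their outcomes may be correlated. Because class is set by arm, any difference between classes goes straight into the arm contrast, while a standard error computed from individuals leaves it out. The stated interval is then too narrow and the test rejects too often.

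The second issue is interpretation. Section 2.2 explains that the diet is held the same in both arms so that mindfulness is what is being tested. The same diet content taught by different people in the two arms would not fully achieve that, given the team's own experience. At stake is how far an R61 arm difference in craving-related eating can be taken as evidence on the mechanism, and what is carried into R33 planning.

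**Working it through.** **The plan's own figure.** The plan gives no class-level figure to reproduce. The related figure is the between-arm power in section 9.2: difference 10 points, SD 11, 30 per arm, two-sided 5%, stated power 80%. The standard error is 11 × √(2/30) = 2.84, so power = Φ(10/2.84 − 1.96) = Φ(1.56) = 94%. The stated 80% therefore does not follow from its own inputs. That is a separate matter and nothing below depends on it.

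**Inputs.**
- 3 waves of 20 at 1:1 (section 3). With one class per arm per wave, which is an inference, this gives 3 classes of 10 per arm.
- SD 11 points (section 9.2).
- Class ICC: not in the documents; assumed 0.01 to 0.10.

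**Formulas.**
- Design effect DE = 1 + (10 − 1) × ICC.
- True SE / individual-level SE = √DE. Effective n per arm = 30/DE.
- Actual two-sided error = 2 × [1 − Φ(1.96/√DE)]. Actual one-sided error = 1 − Φ(1.645/√DE).
- SD of the arm difference due to class alone = 11 × √(2 × ICC/3).

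| Assumed ICC | DE | SE ratio | Effective n per arm | Two-sided error | One-sided error | SD of arm difference from class (points) |
|---|---|---|---|---|---|---|
| 0.01 | 1.09 | 1.04 | 27.5 | 6.0% | 5.8% | 0.9 |
| 0.02 | 1.18 | 1.09 | 25.4 | 7.1% | 6.5% | 1.3 |
| 0.05 | 1.45 | 1.20 | 20.7 | 10.4% | 8.6% | 2.0 |
| 0.10 | 1.90 | 1.38 | 15.8 | 15.5% | 11.6% | 2.8 |

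Simulating the ordinary t-test with six classes of 10 and no arm effect (40,000 trials per ICC) gives 5.9%, 7.3%, 10.4% and 15.8% two-sided, and 5.9%, 6.7%, 8.7% and 11.6% one-sided. This agrees with the formulas.

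**Width of a class-adjusted interval.** Six classes and two arms leave 6 − 2 = 4 df, with critical t 2.78 against 2.00 on 58 df, a ratio of 1.39. Multiplied by the SE ratio, this gives 1.39 × 1.04 ≈ 1.4 to 1.39 × 1.38 ≈ 1.9. Fitting wave as well at class level leaves 2 df (t = 4.30): 2.15 × 1.04 ≈ 2.2 to 2.15 × 1.38 ≈ 3.0.

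**Does the missing wave stratum matter?** Blocks of 4 or 6 within two BMI strata were simulated, with an assumed 5% to 20% of participants below BMI 25. The largest departure from 10 per arm in any wave was at most 2 people in about 98% to 99.6% of trials. Arms stay close to balance within waves without stratifying by wave.

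**The case against.** The case on the other side has force on several points.

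- A reader might infer that different diet teachers serve the two arms. The documents do not say so. Section 5.2 describes the diet course once, for everyone, and one educator may well teach both classes, in which case that effect largely cancels. The accurate statement is that the assignment is unspecified.
- The mindfulness instructor is present in one arm only, but that follows from the design, since Ed has no mindfulness session. No model or schedule can remove it.
- Teaching is not left open to anyone. Diet teachers need relevant experience and use a study manual, the mindfulness instructor must be experienced, and app videos and audio deliver part of the mindfulness content identically. This limits teacher variation but does not remove it, and the app does nothing for diet teaching.
- The evidence in section 2.2 is indirect. It comes from people without type 2 diabetes, and the benefits it names are weight, lipids and fasting glucose, not craving-related eating. This is a reason to treat the ICC as unknown, not as zero.
- At an ICC of 0.01 to 0.02 the one-sided error is only about 6% to 7%.
- A reader might infer that the inflation produces a false go-ahead for R33. The documents tie that step to no p-value. R61 seeks preliminary evidence, and section 9.2 puts the within-arm Ed+MBI decrease first. Section 9.6 nevertheless makes the between-group comparison primary, so its standard error matters.
- A reader might also fault the lack of stratification by wave. The simulation shows that it matters little, and wave imbalance is not what would tie teacher to arm.

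**Conclusion.** The point stands as a gap in specification and analysis; no confounding of teacher with arm has been shown. Classes are arm-specific, the team has itself observed teacher variability, diet-teacher assignment is unstated, and neither the between-arm analysis nor the sample size allows for class.

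For R61, a nominal 5% test would run at about 6% to 16% two-sided, or 6% to 12% one-sided. These figures rest on two assumptions: an ICC of 0.01 to 0.10, and one class of about 10 per arm per wave. They describe class effects of any origin and cannot be attributed to diet teachers in particular. The documents do not give the number of classes in R33, so no figure is offered for that phase.

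**What to change.** 1. **Section 5.2:** state that within each wave the same diet educator teaches the diet sessions of both the Ed and the Ed+MBI class. This must be settled before classes start, because analysis cannot repair it afterwards. State also that the mindfulness instructor's effect cannot be separated from the mindfulness content.
2. **Section 9.6:** beside the main result, report the arm difference with a standard error that allows for class, using either a random class effect or a class-level analysis, with small-sample df. Report the class ICC for R33 planning, noting that six classes estimate it imprecisely.
3. **Optional and minor:** stratify by wave or fit wave as a fixed effect. Fitting wave at class level leaves only about 2 df.

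**Cost.** The educator has to be scheduled for two class times per wave; no extra participants are needed. The class-adjusted interval is about 1.4 to 1.9 times as wide on 4 df. At the plan's difference of 10 and SD of 11, a two-sided class-level test has power of about 72%, 60% and 49% at ICCs of 0.01, 0.05 and 0.10. It should therefore be a sensitivity result and not a gate for proceeding.

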3. STUDY DESIGN

This is a two-phase study. Both phases will use a randomized, controlled trial design. After pilot testing in the first phase, the second phase will include employing an adaptive intervention design in the post-treatment phase to test optimization of the maintenance intervention (i.e. assigning maintenance intensity/dose based on how a participant is doing).

We will use ecological momentary assessment (EMA) methods to measure eating in response to difficult emotions and/or food cravings. In the R61 phase, we will ensure this measure is appropriate for further testing and assess the impact of the MBI components on our hypothesized behavioral mechanisms in N=60 community-dwelling adults with T2DM. We plan 3 waves of 20 persons each with 12 weekly sessions followed by 3 monthly maintenance sessions, to be held at UCSF Osher Center for Integrative medicine. All participants will attend an in-person group course providing education on basic behavioral strategies for diet and physical activity. Participants will be randomized (1:1 ratio) to receive this education alone (Ed) or this same material with added MBI components (Ed+MBI). We will also pilot test two levels of intensity of maintenance phase intervention (monthly group meetings alone or supplemented by individualized attention) to prepare them for R33 testing. Assessments will be done at 0, 3 and 6 months. Study participation lasts approximately 8 months per participant. The R61 phase of the study is 2 years total.

We plan an R33 phase trial in which 120 persons with T2DM will be randomized (using a 1:2 ratio) to Ed or Ed+MBI conditions and followed for 12 months, including a 9-month maintenance phase. We will test the robustness of the effect of MBI components on our proposed behavioral mechanisms, and on dietary adherence, as well as preliminary effect sizes on weight and glycemic control. We will use an innovative adaptive intervention design to optimize maintenance phase intensity, which we believe may be key to augment the MBI effects. For this phase, assessments will be conducted at 0, 3, 6 and 12 months, with study participation lasting approximately 14 months per participant, and the entire r33 phase lasting 3 years.

In both phases, randomization will be done using blocked randomization to ensure approximately equal group sizes, with randomly selected block sizes and will be stratified by BMI (below and above

25, i.e. normal vs. overweight/obese). Neither participants nor study personnel will be blinded to treatment arm.

Primary mechanistic outcome(s): Our primary hypothesized mechanism is reduction in **frequency of eating in response to cravings** as a result of enhanced ability to address food cravings with mindfulness training. Our key measure of this mechanism is frequency of eating in response to cravings using ecological momentary assessment (EMA).

4. SELECTION AND ENROLLMENT OF PARTICIPANTS

4.1 Inclusion Criteria

Participants must meet all of the inclusion criteria to participate in this study:

1. History of T2DM mellitus. If taking insulin, screening labs will include C-Peptide to rule out T1DM. The study intervention is not designed for people with Type 1 diabetes who make no insulin.
2. HbA1c > 6.5% and < 12.0% at screening. The lower limit confirms the diabetes diagnosis. Persons with a HbA1c > than 12% typically need immediate attention to the medical regimen, and we aim to have this done before entering the trial to better separate the effects of improved medical regimens from the diet intervention. Potential participants with a HbA1c > 12% can be enrolled once glucose control is improved.
3. Experience food-related cravings most days of the week and eat in response to these cravings regularly. A key hypothesis is that our mindfulness approach will reduce cravings and craving-related eating, and this is primary mechanistic outcome. Thus we need to recruit participants who experience this.
4. Aged 18 years old and older. We are not enrolling younger children as they may need an intervention that is better tailored to children.
5. Able to engage in light physical activity. We will be recommending physical activity as part of the intervention.
6. Willing and able to participate in the interventions. Must be interested in following a carbohydrate- restricted diet, willing to learn about mindful eating and behavioral strategies for following prescribed diets, have sufficient control over their food intake so that they can follow either diet, and otherwise be able and willing to participate in the intervention. Intervention content must be practiced to evaluate whether it is effective.
7. Have smartphone and are willing to use it on a regular basis for data collection (e.g. craving EMA assessment).
8. Ability to speak English. Groups will be conducted in English, and we do not have the capacity, given the resources available in this proposal, to translate all course material and conduct groups into another language. We enrolled Hispanic participants into the pilot study who were fluent in English, and expect to do this in the proposed study.

4.2 Exclusion Criteria

Candidates meeting any of the exclusion criteria at baseline will be excluded from study participation:

1. Unable to provide informed consent.
2. A substance abuse, mental health, or medical condition that, in the opinion of investigators, will make it difficult for the potential participant to participate in the intervention or that may need immediate changes in medical management that will affect study outcome measures. Such conditions may include cancer, liver failure, renal failure, untreated hypo or hyperthyroidism,

- or history of serious bulimia. The study will be conducted in a group setting, and persons with significant substance abuse or mental health conditions that interfere with social functioning in a group setting may be disruptive. Other medical or mental health conditions that need immediate changes in management, such as thyroid disorders, need to be addressed before starting the intervention so that more reliable baseline measurements can be made prior to beginning the intervention. Some other serious medical conditions that may alter key study outcomes or require other important diet modifications, including untreated hypothyroidism, renal failure, cirrhosis, and conditions requiring oral or parenteral glucocorticoid treatment.
3. Pregnant or planning to get pregnant in the next 6 months, breastfeeding or less than 6 months post-partum. The intervention is not designed for the particular diet considerations during pregnancy and breast-feeding.
 4. Current use of weight loss medications, such as Alli or amphetamine-based drugs that may affect weight. These treatments may make it difficult to discern the effects of the intervention on outcomes such as weight.
 5. Planned weight-loss (bariatric) surgery or bariatric surgery within the past 18 months. Bariatric surgery is likely to change study outcome measures, making it difficult to distinguish the effects of the intervention program.
 6. Currently enrolled in a weight loss program, such as Weight Watchers or a self-help group such as Overeaters Anonymous, or have unalterable plans to enroll in one of these programs in the next year. These plans may contaminate study intervention outcomes and provide participants with mixed messages about their diet.
 7. Vegan or vegetarian. The carbohydrate-restricted intervention diet is more challenging for vegan or vegetarian participants and needs particular tailoring that is difficult to address in adequate detail in a group setting.
 8. Unwilling to do home ketone monitoring.

